24.1 Study Intervention(s) Administered

24.1.1 Investigational Products

AZD4573 will be administered as an absolute (flat) dose, 2-hour (\pm 15 minutes) IV infusion once weekly, at least 5 days apart, alone and in combination with acalabrutinib 100 mg twice daily continuously.

AZD4573 and acalabrutinib will be supplied by AstraZeneca. CC1

Detailed

information on the drug products and administration guidelines are in the AZD4573 Handling Instructions and acalabrutinib participant leaflet.

Table 28 Investigational Products

Intervention Name	AZD4573	Acalabrutinib
Type	Drug	Drug
Dose Formulation	Concentrate for solution for infusion	Capsules
Unit Dose Strength(s)	1.5 mg/mL	100 mg
Dose	Part A Period 1: 12 mg* Part A Period 2: dose to be established based on emerging data from Module 1	100 mg BID
Route of Administration	IV infusion	Oral
Use	Experimental	Experimental
IMP and NIMP	IMP	IMP

Intervention Name	AZD4573	Acalabrutinib
Sourcing	Provided centrally by AstraZeneca	Provided centrally by AstraZeneca
Packaging and Labelling	Study Intervention will be provided in vials. Each vial will be labelled as required per country requirement	Study Intervention will be provided in bottles. Each bottle will be labelled as required per country requirement
Current/Former Name(s) or Alias(es)	AZD4573/ AZ13810325	Acalabrutinib/ACP-196 /Calquence

*In Period 1, target dose of 12 mg achieved through intra-patient ramp up from starting dose on Day 1 (6 mg), with subsequent titration to the intermediate dose on Day 8 (9 mg), and to target dose of 12 mg on Day 15.

Abbreviations: BID = twice daily; IMP = investigational medicinal product; IV = intravenous;
NIMP = non-investigational medicinal product.

Labels will be prepared in accordance with Good Manufacturing Practice and local regulatory guidelines and will be translated into the local language. The labels will fulfil Good Manufacturing Practice Annex 13 requirements for labelling.

All IPs should be kept in a secure place under appropriate storage conditions. The IP label on the vial (AZD4573) or bottle (acalabrutinib) specifies the appropriate storage conditions.

Participants enrolled in this study module will receive AZD4573 alone and in combination with 100 mg acalabrutinib. Acalabrutinib is intended to be administered orally every day, twice daily with approximately 240 mL of water and can be administered without regard to food. Doses should be administered 12 hours apart (a window of \pm 1 hour is allowed) at approximately the same times each day. The acalabrutinib capsules should be swallowed intact. Participants should not attempt to open capsules or dissolve in water. If vomiting occurs after taking acalabrutinib, the participant should not retake acalabrutinib until the next scheduled dose.

On the day of PK collection, acalabrutinib capsules should be brought to site by the participant and taken within 5 minutes before initiation of AZD4573. The actual date and time of AZD4573 and acalabrutinib dosing will be recorded.

If an acalabrutinib dose is not taken within the allowed window, it can be taken up to 2 hours after the scheduled time with a return to the normal schedule the same or following day. If it has been $>$ 2 hours, the dose should not be taken, and the participant should take the next dose at the next scheduled time. The missed dose will not be made up and must be returned to the site at the next scheduled visit. If a participant needs to take a dose earlier than scheduled, the participant can take the dose up to 2 hours earlier than the scheduled time except on scheduled site visit days. Participants should make every reasonable effort to take the acalabrutinib on

time. Guidance on co-administration of acalabrutinib with agents that affect gastric pH is provided in Section [24.8](#).

24.2 Starting Dose, Dose-Escalation Scheme, and Stopping Criteria

Module 2, Part A, Period 1 will confirm in MCL the AZD4573 monotherapy RP2D dose, established in DLBCL in the FTIH study (D8230C00001), as the dose setting in the FTIH study did not include MCL participants. The AZD4573 monotherapy RP2D is 12 mg once weekly with an intra-patient ramp over 3 weeks (1st week 6 mg; 2nd week 9 mg; 3rd week and onwards 12 mg).

In Module 2, Part A, Period 2, the dose of AZD4573 administered in combination with acalabrutinib will be established based on emerging data from Module 1 and will be a dose deemed by the SRC to be tolerated in combination with acalabrutinib in participants with DLBCL (ie, the RP2D in DLBCL).

A study-specific SRC in accordance with its charter, will be responsible for providing ongoing safety surveillance of the study, with regularly scheduled reviews of safety, PK, and other relevant data (see Section [18.6](#)). The SRC will be responsible for making recommendations regarding the conduct of the study.

At any timepoint during the study, the occurrence of a fatal AE deemed related to study therapy (after full etiological work-up and in discussion with the SRC) will result in accrual stoppage and a comprehensive review of safety. In addition, potential safety signals arising from Grade ≤ 4 treatment-related AEs will be reviewed in the context of the overall benefit/risk. On review any event deemed to adversely affect overall benefit risk will trigger an ad hoc SRC for comprehensive safety review.

In the case of PHL, if bilirubin remains elevated (compared to baseline) at 96 hours (-2/+12 hours) after the start of the infusion, the participant must be discontinued from the study and biochemistry followed until resolution. The Sponsor must be notified immediately.

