Assessment	Screen ^a	Period 1 AZD4573 Monotherapy									Disease Assessment ^b /End of Treatment ^{kk}	30-Day SFU ^c	LTFU	Details in CSP Section	
		Cycle 1 Weeks 1 - 5					Cycles 2-8 (Cycle = 21 days)			Cycles 9+ (Cycle = 21 days) ⁱⁱ					
		Days			Days			Day							
1	8	15	22	29	1	8	15	1							
		(\pm 2 Days)					(\pm 2 Days)			(-2 to +5 Days)	(\pm 7 Days)	(\pm 7 Days)			
CCl sample for CCl isolation ^{dd}	(X)	X (pre-dose)													Section 26.10.4.1
Genomics Initiative saliva sample (optional) ^{ee}	(X)	X (pre-dose)	(X)	(X)	(X)	(X)	(X)	(X)	(X)	(X)	(X)	(X)			Section 26.11
Tumour biopsy sample (optional) ^{ff}											At disease progression	(X) ^{ff}			Section 26.10.2
Bone marrow biopsy & aspirate ^{gg}	X										As clinically indicated and to confirm CR				Section 26.4.3 and Section 26.10.3
Disease assessment ^b and radiologic scans ^{hh}	X	See Table 37 schedule										X			Section 26.4.2
AZD4573 intravenous ⁱⁱ		Once weekly (from Cycle 1, Week 1 to end of treatment) ^{ll}													Section 24.1
Disease progression follow-up (SoC)													X		Section 26.1.9.2
Survival Follow-up													X		Section 26.1.9.3

^a Screening tests should be performed within 30 days before the first administration of study drug, unless otherwise indicated.

- b Disease assessments will be done by the Investigator using the Lugano Response Criteria for Non-Hodgkin's Lymphoma ([Cheson et al 2014](#)). Additional disease assessments may be performed as clinically indicated.
- c The SFU visit will be performed 30 days (± 7 days) after the last dose of all study drug. Tumour assessments will be repeated at this visit if they have not been performed within 9 weeks if the participant discontinued before or during Week 26, or 12 weeks if the participant discontinued after Week 26.
- d Informed consent must be obtained ≤ 30 days before the first dose of study drug and must be obtained before any protocol-defined screening procedures are done.

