- k ECHO should be done at Screening and within 14 days after an abnormal ECG finding (eg, T-wave inversion/flattening) or as soon as possible when clinically indicated. If an ECHO cannot be taken, a MUGA scan to assess LVEF will be done. In case of any T-wave abnormality, the ECHO (or MUGA) should be repeated at the 30-day follow-up visit to address the question of recovery, during the off-treatment period.
- l Haematology testing should be measured at Screening, Cycles 1, 2, and 3 predose (within 72 h prior to infusion) and 24 h after the start of the infusion. From Cycle 4 onwards, haematology testing should be predose (within 72 h prior to infusion) and (if clinically indicated) 24 h after the start of the infusion. A sample will also be drawn at the 30-day SFU. The Investigator may take additional, unscheduled samples throughout the study if deemed clinically warranted and these need to be entered into the eCRF. Haematology tests do not need to be repeated before first dose if the first-dose visit is within 3 days of the Screening sample.
- m Coagulation testing should be measured at Screening, Cycles 1, 2, and 3 predose (within 72 h prior to infusion) and 24 h post-infusion of AZD4573. For Cycles 4-8, predose (within 72 h prior to the infusion); the 24-h sample can be omitted unless clinically indicated. For Cycles 9+, on Day 1 of each cycle, an AZD4573 pre-infusion sample will be drawn within 72 h prior to infusion. A sample will also be drawn at the 30-day SFU. The Investigator may take additional, unscheduled samples throughout the study if deemed clinically warranted and these need to be entered into the eCRF.
- n Clinical chemistry should be measured at Screening, Cycles 1, 2, and 3 predose (within 72 h prior to infusion), and 24 h post-infusion of AZD4573. From Cycle 4 onwards, clinical chemistry testing should be measured predose (within 72 h prior to infusion) and (if clinically indicated) 24 h after the start of the infusion. A sample will also be drawn at the 30-day SFU. The investigator may take additional, unscheduled samples throughout the study if deemed clinically warranted and these need to be entered into the eCRF. Clinical chemistry tests do not need to be repeated before first dose if the first-dose visit is within 3 days of the Screening sample.

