cc Exploratory blood **CCI** [REDACTED] Whole blood samples will be collected at Screening and Cycle 1 Weeks 1-3 at predose (within 2 h prior to dosing), 2 h (\pm 15 mins) and 24 h (\pm 2 h) after the start of the infusion and on Day 1 of Cycles 2, 3, 5, and 7 predose (within 2 h prior to dosing), and at every scheduled or unscheduled tumour assessment scan (if on the day of infusion, collect pre-infusion), and at disease progression/end of treatment. If a sample is not taken at End of Treatment, a sample should be obtained at the 30-day SFU.

dd **CCI** sample for **CCI** [REDACTED] isolation will be collected at Cycle 1, Week 1 predose.

ee An optional saliva sample for genomics initiative research will be taken from consenting participants prior to the first dose of IP. If for any reason the sample is not taken before dosing it may be taken at any visit until the last study visit. Only one sample should be collected per participant for genetics during the study.

ff A biopsy will be taken at disease progression for participants who consent. The disease progression sample may be taken at the SFU visit if not collected previously.

gg Bone marrow biopsy and aspirate: **CCI** [REDACTED]

hh See [Table 37](#) for schedule of disease assessments, including mandatory PET assessments. Disease assessments will be done by the Investigator using the Lugano Response Criteria for Non-Hodgkin's Lymphoma ([Cheson et al 2014](#)). Additional disease assessments may be performed as clinically indicated.

ii AZD4573 is to be administered as an absolute (flat) dose, 2-h (\pm 15 mins) IV infusion on a once-weekly schedule.

jj If a participant is attending Cycle 9+ visits according to a modified schedule, in which AZD4573 is not infused and assessments are not performed every week, the Day 1 assessments should be performed at least once per cycle.

kk The End of Treatment visit is the last visit attended by the participant prior to the 30-Day SFU on the study. At this visit, the participant does not receive IMP and should undergo the applicable assessments associated with the Cycle and visit they have reached, plus those shown in the "Disease Assessment/End of Treatment" column of the SoA.

ll AZD4573 should be administered at least 5 days apart

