Event ^a	Action	
	AZD4573	Acalabrutinib
	3rd occurrence Discontinue AZD4573	acalabrutinib was withheld, restart acalabrutinib at current dose level at the 1st occurrence and with 1 level dose reduction at the 2nd occurrence . Discontinue acalabrutinib at the 3rd occurrence .
Concurrent elevations in ALT, AST, or bilirubin (Please also refer to Appendix E for actions to be taken in the event of PHL)		
ALT or AST $\geq 3 \times$ ULN with TBL $\geq 2 \times$ ULN (PHL) AND INR $\geq 1.5 \times$ ULN (or $\geq 1.5 \times$ baseline if elevated at baseline) of any duration	Discontinue AZD4573.	Discontinue acalabrutinib.
ALT or AST $\geq 3 \times$ ULN with the appearance of fatigue, nausea, vomiting, right upper quadrant pain or tenderness, fever, rash, and/or eosinophilia $> 5\%$	Discontinue AZD4573.	Discontinue acalabrutinib.
ALT or AST $\geq 3 \times$ ULN and TBL $\geq 2 \times$ ULN where TBL does not return to baseline level within 96 hours (-2/+12 hours) from start of dose and/or AST or ALT do not return to baseline level within 7 days from start of dose	Discontinue AZD4573.	Discontinue acalabrutinib.
Grade 3 elevation ($\geq 5 \times$ ULN) in ALT or AST with TBL elevation above baseline level or ULN, but $< 2 \times$ ULN that do not return to baseline level within 7 days	Discontinue AZD4573.	Discontinue acalabrutinib.
ALT and AST $\geq 3 \times$ ULN with concomitant TBL $\geq 2 \times$ ULN, NO increase in INR $\geq 1.5 \times$ ULN (or $1.5 \times$ baseline), and NO fatigue, nausea, vomiting, right upper quadrant pain or tenderness, fever, rash, and/or eosinophilia $> 5\%$	If recovered to Grade ≤ 1 or baseline level within 96 (-2/+12) hours, rechallenge at same dose level ^c	Withhold acalabrutinib until recovered. Once recovered, restart acalabrutinib at same dose.

^a Adverse reactions are graded using National Cancer Institute CTCAE version 5.0. All grades refer to CTCAE grading except for TLS, which uses the Howard modification of Cairo-Bishop criteria ([Howard et al 2011](#)).

- ^b Elevations in ALT or AST are considered isolated if bilirubin remains below Grade 1, and elevations in bilirubin are considered isolated if ALT and AST remain below Grade 1.

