25.1 Discontinuation of Study Intervention

See the SoA for data to be collected at the time of intervention discontinuation and follow-up and for any further evaluations that need to be completed.

Please refer to Section [7.1](#) for information on discontinuation of study intervention.

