25.2 Patient Withdrawal from the Study

Please refer to Section [7.2](#) for information on participant withdrawal from the study.

In addition for Module 2, participants who experience an AE during the dosing ramp up (Period 1 Weeks 1-3) that result in inability to complete the dosing ramp up will permanently discontinue AZD4573 and exit the study.

25.3 Procedures for Handling Participants Incorrectly Initiated on AZD4573 or Combination Therapy

Please refer to Section [7.3](#) for information on procedures for handling participants incorrectly initiated on AZD4573 or combination therapy.

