If bilirubin fails to resolve within 96 hours (-2/+12 hours) or transaminases fail to resolve within 7 days, or if the event is associated with significant clotting abnormality or clinical symptoms of liver disease, study treatment must be permanently discontinued (the participant remains on study for the 30-day SFU and long-term follow-up [LTFU] visits), and the event must be immediately communicated to AstraZeneca.

For guidance on treating liver toxicity, please refer to [Table 32](#) of this protocol.

During the course of the study the Investigator will remain vigilant for increases in liver biochemistry. The Investigator is responsible for determining whether a participant meets PHL criteria at any point during the study.

Please refer to [Appendix E](#) for the process to be followed to identify and appropriately report events of PHL. It is not intended to be a comprehensive guide to the management of elevated liver biochemistries.

The Investigator will participate, together with the Medical Monitor, in review and assessment of PHL events to agree whether HL criteria are met. HL criteria are met if there is no alternative explanation for the elevations in liver biochemistry.

The Investigator is responsible for recording data pertaining to PHL/HL cases and for reporting AEs and SAEs according to the outcome of the review and assessment in line with standard safety reporting processes.

Regarding the hepatic toxicity events encountered to date with AZD4573, it has been observed that while the biochemical changes of increased transaminase with concomitant elevation in

bilirubin seen in some participants could be classified as HL by its strict definition, they do not follow a pattern that is consistent with true HL predictive of hepatic injury, and are therefore 'PHL' cases. The events are rapidly resolved and to date have not led to any clinical sequelae or lasting hepatic injury. Repeated dosing with AZD4573 following these events has demonstrated that there is no consistent pattern of recurrence and no consistent increase in severity of the events if they do recur.

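### Module 2 gives two incompatible instructions for bilirubin unresolved at 96 hours: Section 24.2 takes the participant off the study, Section 26.1.10.9 keeps the participant on it

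*Protocol*

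**What the plan says.** Section 24.2 states Module 2's stopping criteria. For PHL with bilirubin still above baseline at 96 hours (-2/+12), the instruction is that "the participant must be discontinued from the study and biochemistry followed until resolution", and the sponsor is to be told at once.

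Section 26.1.10.9, on liver chemistry abnormalities, deals with bilirubin that has not resolved within the same 96-hour window, among other triggers. Its instruction is that "study treatment must be permanently discontinued (the participant remains on study for the 30-day SFU and long-term follow-up [LTFU] visits").

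The schedule of activities ties the safety visit to the end of dosing. Table 23 footnote c reads "The SFU visit will be performed 30 days (± 7 days) after the last dose of all study drug", and Table 24 footnote b sets the same timing for Period 2. Neither footnote makes an exception for toxicity. Footnote kk adds that "The End of Treatment visit is the last visit attended by the participant prior to the 30-Day SFU on the study". Section 25.1 sends sites to that schedule: "See the SoA for data to be collected at the time of intervention discontinuation and follow-up".

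**The concern.** Leaving the study and remaining on it are opposite outcomes. The parenthesis in Section 26.1.10.9 shows that the authors know the difference between stopping treatment and ending participation, so the wording of Section 24.2 cannot safely be dismissed as shorthand. Section 26 also rules out protocol waivers or exemptions, so a site that follows one instruction departs from the other.

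The SFU is at stake. Safety and tolerability are the primary objectives of Module 2 (Table 26). The SFU carries off-treatment adverse event evaluation, vital signs, ECG, haematology, general chemistry, urinalysis and troponin. It also carries a conditional cardiac check: "In case of any T-wave abnormality, the ECHO (or MUGA) should be repeated at the 30-day follow-up visit to address the question of recovery". Long-term follow-up, which collects related serious adverse events, comes after it. Sites that resolve the conflict differently would produce uneven off-treatment safety data for the same event.

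**Working it through.** The protocol gives no figure to reproduce here. The check compares trigger and action, then works out where the SFU falls relative to a Section 24.2 exit.

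**Triggers**
- Section 24.2: PHL, with bilirubin above baseline at 96 hours (-2/+12) from the start of the infusion.
- Section 26.1.10.9: ALT or AST at least 3 × ULN and/or total bilirubin at least 2 × ULN, with bilirubin not resolved within 96 hours (-2/+12). This is wider than PHL but includes it, since Appendix E 2 defines PHL as both elevations together.
- Section 26.1.10.9 does not say what resolved means. The overlap is complete if it means back to baseline. A bilirubin that is unresolved on any reading meets both triggers.

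**Actions**
- Section 24.2: off the study; biochemistry followed to resolution.
- Section 26.1.10.9: off treatment; on study for the SFU and long-term follow-up.

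Both cannot be carried out for the same participant.

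**Timing**
- Exit under Section 24.2: 96 − 2 = 94 h, 94/24 = 3.9 days; 96 + 12 = 108 h, 108/24 = 4.5 days.
- Infusions are at least 5 days apart: 5 × 24 = 120 h, which exceeds 108 h. No further infusion comes before the check, so in Period 1 the index infusion is the last dose.
- SFU window: 30 − 7 = day 23 to 30 + 7 = day 37 after the last dose.
- Smallest gap from exit to SFU in Period 1: 23 − 4.5 = 18.5 days (23 − 3.9 = 19.1 days if exit is at 94 h).
- In Period 2, a later acalabrutinib dose can only move the SFU later. Section 26.1.9.1 counts instead from permanent discontinuation of study drug, which also cannot bring the visit forward.

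The SFU therefore always comes after a literal Section 24.2 exit.

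**What the SFU covers**
Table 26 lists seven primary endpoint components: adverse events, dose modifications, discontinuation due to an adverse event, events of special interest, laboratory data, vital signs and ECG. At least four (adverse events, laboratory data, vital signs, ECG) are scheduled at the SFU. This counts categories and is not a share of data lost, because all of these are also collected during treatment.

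**What survives a literal exit**
- Liver tests with INR, fibrinogen and, where available, D-dimer, repeated until resolution (Sections 26.1.7 and 26.1.10.9).
- Related clinical symptoms and signs, and follow-up serious adverse event forms (Appendix E 4.2).
- Adverse event evaluation in the end-of-treatment column of Tables 23 and 24.
- Vital status, to be sought for everyone who received study drug (Section 26.1.9.3).
- The index event and the discontinuation, since the Safety set holds every treated participant (Table 43).

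**The case against.** The strongest reply is that no sensible site would drop the SFU. Section 24.2 itself continues with biochemistry follow-up, so it does not end all contact, and it sits in the study intervention chapter. The SFU depends on stopping drug rather than on study status. Section 26.1.9.2 exempts only participants who withdraw consent or are lost to follow-up from long-term visits, and Section 26.1.9.3 follows all participants for survival. On this view Section 24.2 is loosely worded and the rest of the protocol corrects it.

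Much of this stands. It makes loss of the SFU a possible result of the wording rather than a certain one, and it keeps the point small. It does not remove the conflict: Section 24.2 is mandatory and nothing in the part of the protocol at hand ranks it below Section 26.1.10.9. Core Sections 7.1 and 7.2, on discontinuation and withdrawal, are not in that part and might settle the meaning.

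A reader might also infer that Table 32 (Section 24.9) is a second contradiction. It is not. For raised transaminases and bilirubin "where TBL does not return to baseline level within 96 hours (-2/+12 hours) from start of dose", its action columns discontinue AZD4573 and acalabrutinib. Those columns can hold only drug actions, and the table is silent on study status.

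Nor do the documents establish the same defect in two similar phrases. Section 24.9 has participants withdrawn from the study when a toxicity has not settled within 21 days. Section 25.2 says that adverse events in the ramp-up which "result in inability to complete the dosing ramp up will permanently discontinue AZD4573 and exit the study". Whether either phrase ends follow-up depends on the core sections just named, and Section 25.2 is a deliberate rule specific to this module.

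**Conclusion.** The contradiction between Sections 24.2 and 26.1.10.9 is real and rests on Module 2 text alone. It is worth correcting because it touches the primary safety objective and the correction is almost free.

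For each affected participant, a literal reading of Section 24.2 puts at risk one scheduled safety visit, at least 18.5 days after exit in Period 1, and the follow-up after it. A reader might infer that all follow-up, or the index event itself, is lost; the provisions that survive a literal exit show otherwise.

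The number affected cannot be given. Table 25 calls self-limiting PHL-type events very common with AZD4573 monotherapy, but no rate is stated for cases unresolved at 96 hours. Against the planned 12 or so participants (Section 27.2), one case is 1/12 = 8.3%. Section 18.5 records that enrolment has been permanently halted, which limits future cases, and the documents do not show how many participants were treated in Module 2. Efficacy in this module is exploratory, so any effect on response or survival estimates is secondary.

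The conclusion assumes that unresolved bilirubin in Section 26.1.10.9 includes bilirubin still above baseline, and that the core sections not at hand do not already say which rule prevails.

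**What to change.** In Section 24.2, replace "the participant must be discontinued from the study and biochemistry followed until resolution" with the outcome already given in Section 26.1.10.9: *study treatment is stopped permanently; the participant stays on study for the 30-day SFU and for long-term and survival follow-up under Section 26.1.9, unless consent is withdrawn; biochemistry is followed to resolution.*

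Table 32 agrees with this and needs no change. Sections 24.9 and 25.2 should be reworded only if core Sections 7.1 and 7.2 show that their phrases end follow-up. The new sentence should not import the scanning rule of Section 26.4.2, which continues scans to progression on the study schedule, because Section 26.1.9.2 follows participants who stop early by standard of care. That difference is a separate matter.

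The cost is one sentence. The visits and contacts already exist in the schedule, and no new sample, visit or analysis is needed.
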